**8.6 Handheld Echo (HHE) Population**

At selected sites in the EU, subjects in Part B and Part C can participate in an optional Handheld Echo (HHE) Sub-Study, where subjects who specifically consent will undergo an additional screening procedure using a portable hand-held ultrasound device to obtain an HHE

In the US, an echocardiogram with LVEF within 6 months of screening is required to demonstrate eligibility. If no echocardiogram is available, subject must undergo an HHE during screening to confirm eligibility.

The HHE population (refer to SAP section 8.2.6) thus consists of EU subjects who signed the IC for participating in the HHE Sub-Study and of US subjects without an available recent echocardiogram at screening that contains an LVEF value.

For this population, the HHE exploratory endpoints as indicated in section 6.2.4 of the SAP will be reported. As HHE results are not available in Part A of the trial, the statistical report for Part C will only report subjects who were enrolled in Part B or MLS Part C of the trial.

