- 6) Evidence of current ongoing myocardial ischemia, such as signs (e.g., significant [e.g., > 2 mm] ST segment elevation or depression on ECG, echocardiographic findings suggestive of acute myocardial infarction), symptoms (e.g., angina pectoris, atypical angina pectoris), and/or being medicated with anti-anginal medication. In addition, subjects with signs of prior myocardial infarction (such as pathological Q waves) who are also taking concomitant medications for angina pectoris should be evaluated for presence of ongoing ischemia.
- 7) History of myocardial infarction (MI) within 3 months of screening
- 8) Known uncorrected severe aortic or mitral valve stenosis. For subjects receiving an HHE assessment at screening (refer to exclusion criterion 5), any moderate or severe valvular disease noted during the HHE assessment is considered exclusionary.
- 9) Hypertrophic cardiomyopathy with outflow tract obstruction. For subjects receiving an HHE assessment at screening (refer to exclusion criterion 5), any moderate or severe hypertrophy noted during the HHE assessment is considered exclusionary.

Other cardiac conditions

- 10) Current diagnosis of persistent AF
- 11) One or more episodes of atrial flutter within 6 months prior to screening or atrial flutter at presentation, except subjects who received ablation for atrial flutter at least 3 months prior to screening and had no subsequent recurrence of atrial flutter prior to screening

INSTANT Study Clinical Study Protocol

Study no. FLE-002

8.0 EU-1 Version Page: 45 of 117

- 12) History of any of the following heart abnormalities:
 - a) Long QT syndrome
 - b) Conduction disease (e.g., second- or third-degree heart block, bundle branch block)
 - c) Diagnosed with sinus node dysfunction (e.g., sick sinus syndrome) and/or one of the following:
 - (i) history of unexplained or cardiovascular syncope,
 - (ii) known bradycardia suggestive of sinus node dysfunction, and/or
 - (iii) prior electrical or pharmacological cardioversion associated with prolonged sinus or ventricular pause (e.g., > 3 seconds) and/or slow ventricular rhythm (e.g., < 45 bpm) at time of conversion
 - Note: Sinus node dysfunction in AF is more prevalent in patients >75 years old.²
 - d) Brugada Syndrome
 - e) Torsades de pointes (TdP)
- 13) Any of the following ECG-related features:
 - a) QTc interval > 480 msec at screening (estimated by the Fridericia's formula¹)

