9.6 B - Handheld echocardiogram (HHE)

To evaluate the subject's eligibility during screening (e.g., LVEF, valvular disease, structural heart disease), a diagnostic echocardiogram with a Sponsor-provided handheld portable ultrasound device will be required at screening for US subjects if the subject does not have results from a standard diagnostic echocardiogram (including LVEF) within the 6 months prior to screening. For information on the HHE Sub-Study available to EU subjects, refer to Section 17.5.

The following data will be recorded from the HHE in the eCRF:

- Date and time HHE is administered
- Who performed the HHE (e.g., professional title or study role)
- Date and time HHE report/results became available
- Who analyzed the echocardiogram obtained (e.g., professional title or study role)
- The following assessments will be recorded:
 - LV size
 - o LVEF
 - LV hypertrophy
 - Valvular disease
 - Other clinically significant findings

The HHE data will be submitted to an independent reviewer to compare with the HHE assessments made by the site staff during the screening period; however, this independent review will not be used for the assessment of Part B subject eligibility during screening. This independent review will only be used to explore if site staff made a successful assessment of subject eligibility using the HHE data obtained during screening.

10 B - Statistical methods

Statistical analyses for Part B will apply to all Part B subjects, including those EU subjects participating in the Handheld Echo Sub-Study (refer to Appendix 6). Data from the HHE Sub-Study are collected on a subset of the Safety Population for Part B and the Part C Medically-Led Cardioversion Study. The analysis for the additional echocardiogram data measured will be separate from the safety analyses of all Part B subjects and Part C subjects in the Medically-Led Cardioversion Study.

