17.5.3.2 HHE Sub-Study Evaluation

After providing informed consent for this Sub-Study, subjects will undergo a diagnostic echocardiogram using a Sponsor-provided handheld portable ultrasound device (HHE). The site staff will evaluate the subject's echocardiogram for any structural heart and functional abnormality. Subjects with exclusionary valvular or structural heart disease (as per exclusion criteria, refer to Section 4.2 B) or clinically significant enlarged LV or decreased EF observed on the echocardiogram will be considered ineligible for enrollment and recorded as screen failures.

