**9.1 Patient Disposition, Demographic and Baseline Characteristics**

Patient disposition will be presented for all subjects who signed Informed Consent, i.e., Population of Consented Subjects. The number of subjects who completed the study and discontinued from the study will be summarized. The reasons for early discontinuation at any time in the study will be described by dose cohort. Screen failures are defined as subjects who signed Informed Consent but were not enrolled (randomized or allocated).

Disposition, demographic and baseline characteristics data, including age, gender, race, ethnicity, etc. will be summarized in tables for each MLS population and cohort as described in Section 8, but no statistical testing will be performed.

Medical history and AEs will be coded using the Medical Dictionary for Regulatory Activities (MedDRA) (version 23.1 or higher) for the study period. Medical history and AEs may be summarized in tables and will be presented in data listings.

Prior and concomitant medications will be coded using the World Health Organization (WHO) Drug Dictionary (version WHO September 2019 or later). Prior and concomitant medications may be summarized in tables and will be presented in data listings.

A separate consort diagram will be provided for the pooled analysis (Part A, part B and Part C MLS) and for Part C PLS.

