### **9.2.4.3 *Subject considered ineligible as a result of HHE assessment***

The independent review will not be used for the assessment of subject eligibility during screening. For this endpoint therefore only investigator reported information is used.

As a result of is interpreted in the SAP as: the HHE assessment is the main reason for subject being non-eligible for enrollment. For all subjects who are ineligible for enrollment investigator fills out maximum three failed Inclusion/Exclusion Criteria in the EDC, the first one filled out is considered to be the *main reason*. Thus, if as first failed IC/EC Criteria Exclusion above cited Inclusion criteria 5 is indicated, the HHE is the main reason for subject.

The endpoint is thus met if these two conditions both apply:

- HHE analysis performed by investigator indicates subject is considered ineligible (refer to SAP section 9.2.5.2) *and*
- The HHE assessment is filled out by investigator in the EDC as being the main reason for subject being ineligible in the trial.

The endpoint is reported for subjects included in the HHE population for whom the HHE assessment resulted in the conclusion ‘Eligible’ or ‘Non Eligible’, meaning subjects are excluded if assessment resulted in “Not Assessable”.

For these subjects the number of and percentage of subjects who were classified as “Ineligible” are reported, as is the number and percentage of subjects who meet the endpoint (being “Ineligible” with the HHE Echo results as main reason for being Ineligible for enrollment).

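### The SAP attributes ineligibility to the handheld echo through a criterion 5 that does not match protocol V8.0 EU-1, and its wording on who is reported conflicts with its own HHE population

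*SAP*

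**What the plan says.** **Reason code.** SAP 9.2.4.3 sets two conditions: the investigator's HHE makes the subject ineligible, and the HHE is the main reason for ineligibility. The investigator may enter up to three failed criteria, and the first is taken as the main one. The rule then reads: "if as first failed IC/EC Criteria Exclusion above cited Inclusion criteria 5 is indicated, the HHE is the main reason for subject". The criterion meant is the one reproduced in SAP 9.2.4.2, a single item requiring adequate LVEF, no more than mild hypertrophy and no more than mild valve disease. It is attributed to protocol section 4.2 B.

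Protocol V8.0 EU-1, section 4.2 B, is arranged differently. Criterion 5 is an exclusion for significant heart failure, with four parts: recent hospitalization, LVEF below 45%, NYHA class and medication history. HHE valve findings are in criterion 8. HHE hypertrophy is in criterion 9, where "any moderate or severe hypertrophy noted during the HHE assessment is considered exclusionary".

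**Population.** SAP 8.6 says the HHE population "thus consists of EU subjects who signed the IC for participating in the HHE Sub-Study and of US subjects without an available recent echocardiogram". The section ends by saying that "the statistical report for Part C will only report subjects who were enrolled in Part B or MLS Part C of the trial", and the reason given is that Part A has no HHE results. Protocol section 10 B states: "Data from the HHE Sub-Study are collected on a subset of the Safety Population for Part B" (and the Part C Medically-Led Study). Under protocol 17.5.3.2, subjects with exclusionary findings on the echo "will be considered ineligible for enrollment and recorded as screen failures".

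**The concern.** The percentage ineligible because of the HHE is one of three exploratory HHE endpoints in protocol 7.5.3 B, and the one that shows whether screening with the device changes who enters the trial. It depends on two things: which subjects are in the set, and which recorded reason counts as the HHE. The SAP leaves a doubt on each.

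The reason rule points to a criterion that the governing protocol does not contain in that form. SAP 1.1.1 says the plan follows V8.0 EU-1, and SAP section 10, which lists departures from that version, does not mention this one. A programmer applying the rule to V8.0 codes would miss some HHE failures and could credit the HHE with others.

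The population wording can be read in two ways. On one of them the endpoint could never be other than zero.

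**Working it through.** The documents state no sample size, precision or expected value for this endpoint, so there is no figure of the plan's own to reproduce. The check sets the sections side by side and then counts.

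**Step 1. Match the SAP's ineligibility conditions to V8.0 criteria.**

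| Condition in SAP 9.2.4.2 | V8.0 exclusion | Counts under 'criterion 5 first'? |
|---|---|---|
| LVEF below 45% | 5(b) | yes |
| Moderate or severe hypertrophy | 9 | no |
| Moderate or severe aortic valve disease | 8 | no |
| Moderate or severe mitral valve disease | 8 | no |

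Three of the four conditions fall under codes other than 5. The rule can also err the other way. Parts (a), (c) and (d) of criterion 5 have nothing to do with the echo. A subject whose HHE shows moderate valve disease, but whose first code is 5 because of NYHA class, would satisfy both conditions of SAP 9.2.4.3.

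**Step 2. Size of the reason-code error on the consent-based population.** Input: 6 HHEs performed (SAP 1.3). Assumptions: all 6 are assessable; k of them are HHE failures; j of those k have a code other than 5 entered first. The documents give neither k nor j.

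- HHE failures: k/6
- Reported under the rule: (k − j)/6
- k = 1: 1/6 = 16.7% (exact 95% CI 0.4 to 64.1). With j = 1 the rule gives 0/6 = 0%.
- k = 2: 2/6 = 33.3% (4.3 to 77.7). With j = 0, 1, 2 the rule gives 33.3%, 16.7%, 0%.
- k = 0: 0/6 = 0% (0 to 45.9), and the rule makes no difference.

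**Step 3. What a literal reading of 'enrolled' would do.** SAP 9.1 defines a screen failure as someone who consented but did not reach enrollment. Protocol 17.5.4.1 bars enrollment until the echo has been evaluated. An HHE failure handled per protocol is therefore never enrolled, and the enrolled-only result is 0/(6 − k): 0/5 for k = 1, 0/4 for k = 2, 0/3 for k = 3. The numerator is zero for every k. The investigator 'No' row of the agreement table in SAP 9.2.4.5 would also be empty. The Safety Population in protocol 10 B has the same consequence, because it requires inhalation to have started.

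**Step 4. Does the rest of the SAP support that reading?** It does not. The population in 8.6 is set by Sub-Study consent or by lack of a recent echocardiogram, both of which are screening-stage conditions. SAP 9.2.4.3 takes everyone in that population with an Eligible or Non Eligible result and adds no enrollment condition. Its source is the failed-criteria entry made for subjects who cannot be enrolled.

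**The case against.** The strongest reply is that both problems are loose wording. The sentence in SAP 8.6 gives its reason, the absence of HHE data in Part A, so 'enrolled in' probably just names the study parts. The Safety Population phrase appears only in the protocol, which leaves specifics to the SAP. On the reason code, SAP 9.2.4.3 refers to the combined criterion as cited in 9.2.4.2, and on those terms all four conditions belong to it. Its formal second condition asks only whether the HHE was entered as the main reason, without a number. Criteria 8 and 9 themselves refer back to 5. HHE subjects could enter under V7.0/EU-1 or later, and neither that version nor the EDC code list is among the documents. Finally, SAP 9.2.4.3 also reports everyone classified as ineligible, whatever the code.

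Most of this stands as a limit on the point. A reader might infer that the endpoint is confined to enrolled or Safety subjects and biased to zero. The documents do not support that: Step 4 shows that the operative section includes screen failures, and the SAP does not repeat the Safety restriction. A reader might also infer that only a low LVEF could ever count. That too goes beyond the documents, given the combined criterion the SAP cites and the non-echo parts of criterion 5.

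The reply does not remove the mismatch. The SAP names V8.0 EU-1 as its basis, and the cited criterion is not there. The count of all ineligible subjects softens the error, but it is not the endpoint.

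**Conclusion.** The reason-code defect holds. If failures are coded by V8.0 numbers, an HHE failure entered first under 8 or 9 does not meet the endpoint, and a first code of 5 need not come from the echo. The population wording is a contradiction to reconcile; it does not settle that screen failures are excluded.

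The effect is small. The endpoint is exploratory, 6 HHEs were performed, and SAP 9.2.4 places the HHE endpoints in listings, where individual cases can be seen. With one valve failure coded 8, the figure would be 16.7% instead of 0%, with an interval so wide that no inference rests on it. That example assumes a failure occurred, which the documents do not say, that V8.0 codes were used, and that all six scans were assessable. No efficacy or safety result is affected.

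**What to change.** - **SAP 9.2.4.3:** count the endpoint when the investigator's HHE result is Non Eligible and the main (first) failed criterion is the HHE-based part of exclusion 5, 8 or 9. To separate the HHE-based part, match the code to the recorded finding: 5 with LVEF below 45% on HHE, 8 with moderate or severe valve disease, 9 with moderate or severe hypertrophy.
- **SAP 9.2.4.2:** replace the citation of a combined inclusion criterion 5 with exclusions 5, 8 and 9 of protocol V8.0 EU-1.
- **SAP 8.6:** in the last sentence, replace 'enrolled in' with 'screened for Part B or Part C MLS, including HHE screen failures', and note that this overrides the description in protocol 10 B.
- **Cross-references:** SAP 8.6 points to a section 8.2.6 that does not exist, and 9.2.4.3 points to 9.2.5.2, which concerns patient-led feasibility. Both can be corrected in the same edit.

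The cost is SAP wording and a few lines of programming. SAP 9.2.4.3 says the failed criteria are entered in the EDC, and SAP 5.7 says the same of the investigator's HHE assessments, so no new data are needed. Part C MLS enrollment has stopped, so a note in the SAP is enough and the protocol need not be amended.

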**8.7 MLS Study Population Cohorts****8.7.1 Part C MLS Cohort (Cohort 1)**

This Cohort includes all subjects in the study population (i.e., safety, mITT etc.) who were enrolled in the Part C MLS. This Cohort will be referred to as Cohort 1.

**8.7.2 Pooled MLS Cohort (Cohort 2)**

This Cohort includes all subjects in the study population (i.e., safety, mITT etc.) who were enrolled to receive the 120 mg (2 x 60 mg) FlecIH-103 study medication in Part A, Part B or Part C of the MLS. This Cohort will be referred to as Cohort 2.

**8.7.3 Pooled MLS No Predose Flecainide Cohort (Cohort 3)**

---

## FLE-002 (INSTANT) – Final Analysis

## Statistical Analysis Plan

---

This Cohort includes all subjects in the study population (i.e., safety, mITT etc.) who are part of the Pooled MLS Cohort (Cohort 2) and have no evidence of flecainide present in their predose PK sample. This includes subjects whose pre-dose PK sample had flecainide plasma concentrations = 0 ng/mL and subjects whose pre-dose PK sample was missing. This Cohort will be referred to as Cohort 3.

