**Laboratory values below the limit of quantification**

If a laboratory reports a value below the limit of quantification (e.g., “<0.1” or “BLQ”) the value 0 will be imputed. Additionally, the value 0 will be imputed if the PK value for the sample taken just before initiation (at  $T_0$ ) is not available unless additional information indicates otherwise (refer to SAP section 9.2.2.10).

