### 8.4 PK Population

The PK population includes all enrolled subjects who received the full assigned dose of study drug irrespective of whether the subject was in AF or not at the initiation of dosing. Compared to the Safety population the PK population excludes subjects who did not receive the full assigned dose of study drug. The full 120 mg dose of study medication is defined as completing both inhalation stages, for a total dose of 120 mg eTLD (2 x 60 mg eTLD).

Population includes Part A, Part B and Part C MLS subjects receiving 120 mg FleclH-103.

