**FLE-002 (INSTANT) – Final Analysis****Statistical Analysis Plan****8.5 Modified Intention-To-Treat Population (mITT)**

The modified ITT population includes all enrolled subjects who completed the full assigned dose of study drug and were in AF at the time of start of the inhalation of the study drug. Subjects whose AF converted to SR prior to completion of the assigned full dose of study drug will also be included in the mITT population.

Completing the assigned dose of study medication in accordance with the protocol (i.e., dose/inhale to conversion) is defined as completing both inhalation stages, for a total dose of 120 mg eTLD (2 x 60 mg eTLD), OR completing the dosing early due to conversion of AF to SR. All subjects who converted prior to completion of the assigned 120 mg dose of study medication will be included in the mITT population, regardless if they stopped dosing or continued.

The mITT population will be used to evaluate all primary and secondary efficacy endpoints. Population includes Part A, Part B and Part C MLS subjects receiving 120 mg FlecIH-103.

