### **8.7.4 Pooled MLS Predose Flecainide Cohort (Cohort 4)**

This Cohort includes all subjects in the study population (i.e., safety, mITT etc.) who are part of the Pooled MLS Cohort (Cohort 2) and have flecainide present in their predose PK sample (i.e., flecainide plasma concentrations > 0 ng/mL). This Cohort will be referred to as Cohort 4.

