### 9.2.2.2 *Statistical analysis of time-to-conversion to SR from initiation of dosing up to 90 minutes after initiation of dosing*

The Modified ITT Population will be used for this analysis.

The cumulative incidence for the time to conversion from initiation of study medication up to 90 minutes post dose will be determined using the Kaplan-Meier methods. Subjects who converted within 90 minutes post dose due to adjunct medication or procedure are reported as not converted and will not be censored at the time the subject converted due to the adjunct treatment. Results are shown in a Kaplan-Meier curve.

Kaplan-Meier figures will be created for the following:

- A figure with a single curve, showing results of Part C MLS Cohort (Cohort 1).
- A figure with a single curve, showing results of the Pooled MLS Cohort (Cohort 2)
- A figure with a single curve, showing results of the Pooled MLS No Predose Flecainide Cohort (Cohort 3)
- A figure with two curves, for the Pooled MLS Cohort (Cohort 2) and the Pooled MLS No Predose Flecainide Cohort (Cohort 3)

Analysis will not be performed for the PLS population.

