### **9.2.2.10 Pharmacokinetic (PK) assessment(s): Flecainide plasma concentration over time**

PK results will be reported for all evaluable patients in the PK population. For each subject all available flecainide plasma (PK) values are reported in a listing and in a figure. The PK results are reported according to the time the blood sample was collected since initiation of study medication (minutes). If the PK value for the sample taken just before initiation (at  $T_0$ ) is not available or is reported as 'BLQ' (Below Limit of Quantification) the value 0 will be imputed (unless additional information indicates otherwise).

Section 6.2.5.1 indicates the planned time points PK samples are taken.

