### **9.2.3.2 *Prior and concomitant medication***

In the MLS part of the trial prior and concomitant medications that were taken between 30 days of enrollment through Day 5 of the MLS part of the study is recorded by investigator. For subjects not participating in the PLS Part of the trial this Day 5 visit is the End of Study visit.

For subjects participating in the PLS trial, any additional medications are recorded up to the end of the PLS episode, being either Day 5 of the PLS study (for subject who started PLS study medication, this visit is the EOS visit for subject) or the EOS visit (for subjects who did not start PLS study medication).

All concomitant medications for the reported MLS subjects and Part C PLS subjects will be listed in the statistical report. Additionally, tables will be created to summarize the concomitant medications for the Cohorts defined Table 1 in SAP section 8. For the MLS study, in addition, tables will summarize the medication by type:

- Antiarrhythmics
- Antithrombotics
- Other cardiovascular medication
- Other medication

Additionally tables will summarize the medication by reporting all observed values (before and after start of dosing) of ATC class (e.g. B01AF=DIRECT FACTOR XA INHIBITORS) and within the specific ATC class by reporting all observed values for Standardized Medication name (e.g. Rivaroxaban, Apixaban).

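### SAP 8.7.3 counts every pooled subject with a missing pre-dose PK sample as having no pre-dose flecainide, with no check against recorded flecainide use

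*SAP*

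**What the plan says.** SAP 8.7 splits the Pooled MLS Cohort (Cohort 2) by pre-dose flecainide. For Cohort 3, 8.7.3 states: "This includes subjects whose pre-dose PK sample had flecainide plasma concentrations = 0 ng/mL and subjects whose pre-dose PK sample was missing". Cohort 4, under 8.7.4, takes pooled subjects who "have flecainide present in their predose PK sample (i.e., flecainide plasma concentrations > 0 ng/mL". A missing sample therefore always leads to Cohort 3 and never to Cohort 4.

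Two other sections deal with a missing pre-dose value, but only as a concentration. SAP 7.2.5 imputes 0 when the T0 value "is not available unless additional information indicates otherwise". SAP 9.2.2.10 repeats this for the PK analysis: "the value 0 will be imputed (unless additional information indicates otherwise". Neither says what the additional information would be, and 8.7.3 and 8.7.4 do not refer to either section.

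Cohort 3 has its own place in the results. Table 1 of SAP section 8 lists it for demographics, efficacy, safety, PK and PD. SAP 9.2.2.2 plans "A figure with a single curve, showing results of the Pooled MLS No Predose Flecainide Cohort (Cohort 3", and a second figure that sets it beside Cohort 2.

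**The concern.** The cohort label makes a statement about exposure that the rule does not check when there is no sample. Exposed subjects are expected. Protocol 4.2 B, criteria 3 and 20, keeps eligible those whose current episode was treated with flecainide, up to 320 mg in 24 hours including study drug. The note to Protocol 4.1 B names pill-in-the-pocket flecainide users as a pre-screening group. Cohort 4 exists for such subjects.

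Cohort 3 is where a reader will look for conversion by inhaled flecainide without drug already on board. A wrongly placed subject distorts that view, in a direction the documents do not fix. Earlier drug may add to the effect. Alternatively, a subject still in AF after flecainide may be harder to convert.

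The SAP also allows an odd outcome: a subject could have the zero overridden in the PK analysis because flecainide use is known, and still be tabulated as having none.

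**Working it through.** **1. Can such a subject exist under the text?**

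| Step | Source | Result |
|---|---|---|
| Flecainide for the current episode is allowed | Protocol 4.2 B, criteria 3 and 20 (Parts B and C) | Yes, within the limit |
| That use is recorded | Protocol 5.4.1 B (30 days before enrollment, eCRF); SAP 3.5, Prior Medications | Yes |
| A missing sample is assigned | SAP 8.7.3 | Cohort 3, no condition stated |
| A missing sample can reach Cohort 4 | SAP 8.7.4 | No; a level above 0 is required |
| The override reaches cohort assignment | SAP 7.2.5, 9.2.2.10 | Not stated; it covers the imputed value |

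The current protocol does not give the Part A criteria, so nothing is claimed about Part A exposure.

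**2. Which results could change?** The efficacy column and Kaplan-Meier curve use the mITT population. SAP 8.5 includes early converters: "All subjects who converted prior to completion of the assigned 120 mg dose of study medication will be included in the mITT population". The PK population is narrower: "the PK population excludes subjects who did not receive the full assigned dose of study". It requires two conditions. The first is both inhalations with at least 390 seconds in total; the second is not visible in the text available. An effect on the Cohort 3 PK summary therefore cannot be settled here. Cohorts 1 and 2 do not depend on pre-dose flecainide.

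**3. How large could it be?** The plan gives no figure to reproduce, so this is an illustration. The number of misplaced subjects and the size of Cohort 3 are not given. Part A contributes 27 evaluable FlecIH-103 subjects and Part B about 25, and 27 + 25 = 52. Part C adds an unstated number and Cohort 4 removes some, so sizes of 30 to 70 are assumed. The assumed conversion rate is near the Part A figure of 13/27 = 48%.

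Removing j misplaced subjects from k converters among n changes the rate by (k − j)/(n − j) − k/n if all j converted, and by k/(n − j) − k/n if none did.

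| k/n | j = 1, converted / not (points) | j = 3, converted / not (points) | 90% exact interval width (points) |
|---|---|---|---|
| 14/30 | −1.84 / +1.61 | −5.93 / +5.19 | 32.2 |
| 25/52 | −1.02 / +0.94 | −3.18 / +2.94 | 24.2 |
| 34/70 | −0.75 / +0.70 | −2.30 / +2.17 | 20.8 |

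For example, 14/30 = 46.67% and 13/29 = 44.83%, a difference of −1.84 points.

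**4. Could earlier flecainide still be present?** Protocol 1.2.2 gives an elimination half-life of 9 to 12 hours. Assuming single-exponential decline, the fraction left is 2^(−t/h): at 24 hours, 15.7% (h = 9) to 25.0% (h = 12); at 48 hours, 2.5% to 6.3%. This shows plausibility only. The half-life comes from inhaled dosing in healthy volunteers, and no limit of quantification is given.

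**The case against.** The strongest reply is that the rule is deliberate. Cohort 3 is defined by evidence in the PK sample, and missing samples are addressed openly and mechanically. Section 8.7.3 does not mention the eCRF, so the problem is inferred from the lack of an exception. The rule also matches the imputation in 7.2.5, so the authors may have meant the override to travel with it, leaving only a cross-reference to add. That is possible, but 8.7.3 as written does not say so.

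The affected group is also narrow. It needs flecainide for this episode and a missing sample together. The pre-dose draw may be taken at any time in the 45 minutes before dosing, after enrollment, with a cannula in place. Criterion 28, which excludes flecainide non-responders, may shrink the group further, depending on how it is applied to the current episode. This stands, and it is why the count may be zero.

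The medication tables would expose a misplaced subject: "tables will be created to summarize the concomitant medications for the Cohorts defined Table 1 in SAP section 8". That also stands, but the tables leave the Cohort 3 rate and curve unchanged.

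Moving such subjects into Cohort 4 would mix medication-record cases into a cohort defined by a measured level. This is right, and the fix avoids it. A subject with recorded flecainide and a result below quantification would still stay in Cohort 3. That is defensible, because a sample was taken and showed no quantifiable drug.

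Finally, SAP V5.0 (6 July 2022) postdates the last Part C MLS dosing (7 December 2021) in an open-label trial, so reclassification could add discretion. A fixed rule based on a recorded field, written before the tables are run, keeps that small.

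A reader might infer that Cohort 3 efficacy is inflated by earlier flecainide. The documents do not support that: neither the existence of such subjects nor the sign of any bias can be established.

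**Conclusion.** The point holds as a gap in a stated rule. Section 8.7.3 can place a subject with recorded flecainide for the current episode in the cohort labelled as having none, and the override in 7.2.5 and 9.2.2.10 is not carried into cohort assignment. It should be corrected, but its reach is limited. No formal test depends on it. One misplaced subject would shift the Cohort 3 rate by 0.7 to 1.8 points and three with the same outcome by 2.2 to 5.9, well inside 90% intervals 20.8 to 32.2 points wide. These sizes rest on an assumed Cohort 3 of 30 to 70 and a rate near 48%. A reader might also infer that the Cohort 3 PK results are contaminated. That depends on both PK-population conditions, only one of which can be read, so it is left open.

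**What to change.** In SAP 8.7.3, state that a subject with a missing pre-dose sample stays in Cohort 3 only if the eCRF medication record shows no flecainide for the current AF episode before dosing. If it shows such use, or is unclear, report the subject as unclassified, in neither Cohort 3 nor Cohort 4. Section 8.7.4 then keeps its definition by a measured level. State that the 0 imputed for an unavailable sample is not used for assignment. Report the number of missing pre-dose samples and how each was resolved. Give the Cohort 3 primary endpoint once more with all missing-sample subjects excluded.

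The cost is a short wording change and a check of data already collected. Cohort 3 becomes slightly smaller. For an assumed 52 subjects (25/52), the 90% exact interval widens from 24.2 to about 24.5 points if one is removed (24/51 or 25/51), and to about 25.6 if five are excluded (23/47). The exclusion analysis is an addition, since SAP 7.2.5 plans no sensitivity analysis for other missing values. A subject whose flecainide use was never recorded would still be misplaced in the main Cohort 3 result, but not in the version without missing samples.
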